	11.1 Data protection	
	11.2 Data handling, storage and sharing	
12.	Dissemination of findings	33
13.	References	34
14.	Amendments to protocol	35

Glossary / abbreviations

ADR	Adverse drug reaction
AE	Adverse event - any undesirable event in a subject receiving treatment
	according to the protocol, including occurrences which are not necessarily
	caused by or related to administration of the research procedures.
AR	Adverse reaction – any undesirable experience that has happened a subject
	while taking a drug that is suspected to be caused by the drug or drugs
ATP	Adenosine 5' triphosphate – a multifunctional nucleotide that plays an
	important role in cell biology as a coenzyme involved in intracellular energy
	transfer
BDS	Bis die sumendum: twice daily
BEZA	Bezafibrate
BHI	Bristol Heart Institute
BNF	British National Formulary
BP	Blood pressure
BRI	Bristol Royal Infirmary
BRU	Biomedical Research Unit
BSF	Barth Syndrome Foundation
BSS	Barth Syndrome Service
BTHS	Barth syndrome
CK	Creatinine Kinase
CL	Cardiolipin
CRF	Case report form
CRIC	Clinical Research and Imaging Centre
CTEU	Clinical Trials and Evaluation Unit
DCM	Dilated cardiomyopathy
DMSC	Data monitoring and safety committee
EBV	Epstein-Barr virus
ECG	Graphical representation of electrical activity of the heart over time, as
	recorded by an electrocardiograph
ECMO	Extracorporeal membrane oxygenation
EF	Ejection Fraction
EME	Efficacy and Mechanisms Evaluation programme
EMEA	European Medicines Agency
FS	Fractional shortening
GCSF	Granulocyte colony stimulating factor
GOSH	Great Ormond Street Hospital
GP	General Practitioner
HDL	High density lipoprotein
HUL	High density lipoprotein

HHb	Deoxyhaemoglobin
HMG CoA	3-hydroxy-3-methyl-glutaryl-CoA reductase inhibitors (Statins)
HR	Heart rate
HSG	Health Service Guidelines
ICH-GCP	International Conference for Harmonisation of Good Clinical Practice
IMP	Investigational medicinal product
LA	Left atrial
LDL	Low density lipoprotein
LFT	Liver function test
LV	Left ventricular
LVEF	
LVNC	Left ventricular ejection fraction Left ventricular non-compaction
MedRA	Medical Dictionary for Regulatory Activities
MHRA	
MLCL	Medicines and healthcare products regulatory agency
	Monolysocardiolipin
MRC	Medical Research Council
MRI	Magnetic resonance imaging
MRS	Magnetic resonance spectroscopy
NHS	National Health Service
NIHR	National Institute for Health Research
NIRS	Near infrared spectroscopy
NOS	Not otherwise specified
OD	Omne in die: once daily
PCr	Phosphocreatine
Peds QL [™]	Paediatric quality of life inventory
PIL	Patient information leaflet
PKB	Patients Know Best website (https://www.patientsknowbest.com)
PPAR	Peroxisome proliferator-activated receptors
PW-TDI	Pulse Wave-Tissue Doppler Imaging
RA	Right atrial
RCT	Randomised controlled trial
REC	Research ethics committee
SAE	Serious adverse event - events which result in death, are life threatening,
	require hospitalisation or prolongation of hospitalisation, result in persistent or
	significant disability or incapacity.
SAR	Serious adverse reaction
SmPC	Summary of Product Characteristics
SOP	Standard operating procedure
SPC	Summary of Product Characteristics
SSAR	Suspected serious adverse reaction
SUSAR	Suspected unexpected serious adverse reaction - an untoward medical
	occurrence suspected to be related to a medicinal product that is not
	consistent with the applicable product information and is serious.
TDS	Ter die sumendum: three times a day
TSC	Trial steering committee
UH Bristol	University Hospitals Bristol NHS Foundation Trust
UK	United Kingdom
UoB	University of Bristol
USA	United States of America
VO ₂	Volume of oxygen
WBC	White blood cell count

1. Trial summary

Barth syndrome is a rare, life threatening, genetic disease which affects young males. It is caused by abnormal fats (lipids) in the powerhouses of cells (mitochondria) and those who suffer with it often develop heart failure, heart rhythm abnormalities, bacterial infections, poor growth or feeding, weak muscles, developmental delay, severe exercise intolerance, lethargy and fatigue; all of which affect their daily life. Low white blood cell counts occur frequently due to intermittent or persistent reduction in numbers of the neutrophils that are responsible for fighting bacterial infections. This requires expensive and distressing injections to stimulate the bone marrow to produce more neutrophils. In addition, approximately one third of all males living with this disease in the UK have required heart transplantation.

Scientific research has shown that several treatments can improve the fat abnormalities in cells affected by Barth syndrome from either mice or humans; one of which is a drug called bezafibrate. Bezafibrate is particularly attractive as it has been safely administered for over 20 years in the UK to both adults and children for the treatment of high blood fats. The purpose of this study is to see if bezafibrate can be given safely and effectively to people with Barth syndrome in a blinded randomised trial.

Bezafibrate or an inactive (placebo) treatment will be given for 4 months, followed by a one month break, and then followed by 4 months of the alternate treatment (e.g. placebo if bezafibrate taken for the first 4 months and vice versa). Half of the participants will take bezafibrate first, the other half will take placebo first; participants and research staff will not know which order the treatments are given in (double-blind trial).

Once the participants have completed the first phase of treatment, the study statisticians will be unblinded to the treatment arms and will then assess whether or not there is evidence of efficacy of bezafibrate for the primary outcome.

Tests will be performed at commencement of the study and after each 4 month treatment period, looking for benefit in blood cells, exercise capacity, heart function or quality of life. The clinical studies of bezafibrate will run alongside laboratory work at University of Bristol and Great Ormond St Hospital to see the effect of bezafibrate on participants' cells and mitochondria (powerful electron microscopes show that these are abnormal in Barth syndrome). This is to see whether we can predict any improvement in symptoms in order to tell us which patients would benefit from this treatment in future. Laboratory work will also be carried out on participants' cells using another drug called resveratrol, which has also shown promise in laboratory tests, to see if this could provide an alternative treatment.

We wish to study up to 18 Barth syndrome boys and young men (all of those with Barth syndrome in the UK aged 6 years or over). We aim to use a national children's research network and/or local GPs to perform monthly blood tests in order to minimise the amount of travel to Bristol for participants. Safety will be monitored by an independent committee with the authority to recommend stoppage if obvious problems are seen.

If promising results are obtained with either or both drugs, we would share this information with American/European teams so that this work will have worldwide benefit. For this, we have the complete backing of our patients, their families and the respective UK and USA charities.

2. Background

Barth syndrome is a life threatening genetic disease which affects young males. It is caused by abnormal lipids in mitochondria. Those affected may be stillborn or develop heart failure during the first decade of life, suffer from bacterial infections, poor growth or feeding problems during childhood. Twenty six males and one female are currently alive with the disease in the UK. This disease carries many risks and problems for its sufferers, as well as major healthcare costs.

Boys and men living with the disease have severe exercise intolerance, lethargy and fatigue which affect their daily life; many use wheelchairs intermittently to aid mobility. Furthermore, children continue to die from this disease despite best conventional therapy including granulocyte colony stimulating factor (G-CSF) to stimulate neutrophil production, drugs to treat cardiomyopathy, and cardiac transplantation where required.

Scientific research has shown that several treatments can improve the fat abnormalities in cells affected by Barth syndrome in mice or humans [1]. One is a drug (bezafibrate) that has previously been used in children to lower blood fats as well as in adults with a muscle disease resulting from mitochondrial problems and the other is a food supplement (resveratrol). Both treatments have shown promising effects in a mouse that has heart problems like those seen in Barth syndrome [1].

There are no specific treatments for Barth syndrome other than supportive care provided for acute symptoms. Supplements such as coenzyme Q, carnitine and antioxidants are frequently used to treat other mitochondrial diseases but have proven ineffective in Barth syndrome [2] and there is no evidence that standard medications for cardiomyopathy ameliorate long-term outcome.

30% of living UK patients have undergone cardiac transplantation and several of these have died of cardiac rejection or post-transplant lymphoproliferative disease; others deteriorated too fast to undergo transplantation or died of complications of ventricular assist devices or ECMO whilst awaiting transplantation. In the past five years four babies/infants have been candidates for cardiac transplantation, requiring cumulatively approximately 20 months of intensive care bed stays. Sadly only one has undergone successful transplantation due to factors including shortage of donor hearts. Even those who have not received transplants can develop life-threatening heart rhythm disturbances.

Neutropenia is another life-threatening issue due to attendant serious bacterial infection. As a result, two thirds of UK patients require chronic subcutaneous injection therapy with granulocyte colony stimulating factor (G-CSF), a distressing and expensive medication. Furthermore, the management of neutropenia in this disease is challenging since patients have highly variable neutrophil counts, preventing administration of a consistent daily dose and requiring repeated blood counts and physician oversight. They often remain intermittently neutropaenic even when receiving G-CSF.

Lethargy and fatigue are universal, interfering with schoolwork and play and often necessitating the use of wheelchairs. Similarly patients cannot hold down strenuous or demanding jobs. Many patients have major feeding problems from the neonatal period through into adult life and require long term supplemental feeding via gastrostomies.

There can be rapid deterioration during periods of stable health and when under expert medical care. Ventricular arrhythmia (tachycardia or fibrillation) affects 10% of adolescents and can

cause sudden cardiac death at any stage of childhood, including the neonatal period [3]. These seemingly random acute crises are not predictable by genotype or recent medical history, producing a need for cardiac resuscitation training and chronic anxiety in affected families.

It is clear that more disease-specific therapy is required to prevent morbidity, mortality, psychological distress and disruption of quality of life, potentially producing major savings for the NHS. We in the UK are uniquely well-positioned to explore such therapy, having the world's highest density of diagnosed patients and the only national multidisciplinary service. The NHS Specialised Services Barth Syndrome Service currently cares for 26 living boys and one girl from England, Scotland and Wales (from approximately 200 diagnosed worldwide), of whom 18 are above six years of age and candidates for the trial proposed.

Several of the laboratory and clinical readouts proposed in this study (cardiolipin profiling, cardiac MRS and electron microscopic evaluation of mitochondrial morphology) could have importance for assessing genotype/phenotype correlation and future therapies in Barth syndrome beyond the scope of this randomised trial. Patients with unexplained conditions very closely allied to Barth syndrome are known to this team. The technical expertise developed here may allow better investigation of these patients and those with other unexplained conditions such as idiopathic neutropenia or cardiomyopathy.

'Gold standard' evidence from a randomised controlled trial is now required to investigate the potential risks and benefits of bezafibrate treatment in this population. Prepublication data from [name] et al at New York University (2012) demonstrated clear effects of bezafibrate and resveratrol in partially normalising the highly skewed cardiolipin (CL) ratio that uniquely characterises humans with the disease and Barth mouse knockdown cells [1]. Bezafibrate has since been shown to improve ventricular function at supraphysiological doses in a knockdown mouse model of the disease. This was shown both in cardiomyopathy induced by adrenergic (isoproterenol) stress and by chronic administration in unstressed animals. In the latter it prevented the cardiac deterioration typically seen by 7 months of age [4]. Surprisingly, in contradiction to the previous cellular evidence, this cardiac benefit was not accompanied by improvement of the CL ratio; it is postulated that the drug works via increasing mitochondrial biogenesis (mitochondrial numbers) in cardiomyocytes via a role in activating peroxisome proliferator-activated receptors (PPARs) rather than ameliorating the abnormal lipid chemistry. Bezafibrate has also been shown during a 4-month period at a clinically relevant dose to protect cardiac left ventricular systolic function and, in combination with everyday voluntary running, to significantly ameliorate the impaired exercise capacity in TazKD mice [5].

Bezafibrate is an European Medicines Agency (EMEA) approved lipid-lowering drug with established use in adults and children and a good safety record in long-term use [6]. The BNF recommends doses of 200mg OD to TDS for 10-18 year olds, and Bezafibrate use is well tolerated in younger children in the dose range 5-20 mg/kg/day [7-9] and in adults up to 600-900mg/day [10]. Bezafibrate has been reported to significantly ameliorate a mitochondrial myopathy (CPT2 deficiency) in adults [11] as well as giving promising results in a range of animal/human cellular models of mitochondrial disease.

Resveratrol, a naturally occurring food supplement available from nutraceutical companies, affects energy metabolism and mitochondrial function. Previous human clinical trial data is limited, with mild gastrointestinal symptoms occurring at doses above 1g/day [12]. In a 2011 double-blind crossover trial in healthy obese men resveratrol (at 150mg/day for 30 days) produced a range of statistically significant beneficial clinical effects [13]. Resveratrol has been included for comparative *in vitro* studies because although bezafibrate and resveratrol had

equivalent effects in the mouse model/cells, it had the significantly more convincing effect on improving CL ratio in human Barth syndrome fibroblasts. However, it will not be used in this trial due to NIHR EME Board concerns that its use could aggravate pre-existing neutropenia and that half-life in blood is extremely short.

Barth syndrome is characterised by many private gene mutations; more than 120 have been identified in only 200 affected persons [2]. There is profound phenotypic variability between affected patients within families and those in different families, both in severity of cardinal problems (e.g. cardiomyopathy, neutropenia) and the number of different organs that are significantly affected. There has been no definitive proof of any genotype/phenotype correlation in Barth syndrome.

3. Aims and objectives

We hypothesise that bezafibrate (and/or resveratrol in-vitro) will increase mitochondrial biogenesis and potentially modify the cellular ratio of monolysocardiolipin to L4- cardiolipin, ameliorating disease phenotype in those living with the disease, providing that the drug is free of significant side-effects at clinically effective doses.

The major questions to be answered are as follows:

[figure not shown]
- 1. What is the effect on biochemical/clinical outcome measures and quality of life of bezafibrate treatment in comparison to placebo in Barth syndrome?
- 2. Is it possible to correlate clinical improvements with *in vitro* analysis of cardiolipin ratio/profile and mitochondrial morphology in each participant's cells when exposed to bezafibrate in laboratory culture? How does this contrast with an *in vitro* response to resveratrol exposure? This could indicate whether a trial examining the efficacy of resveratrol may be required in the future to determine the optimal choice of drug.
- 3. What are the most feasible methods and standardised outcome measures that may allow better conduct of future trials (e.g. larger multinational trials) and evaluations in Barth syndrome?
- 4. Is it possible to create a research infrastructure which optimises recruitment, retention and communication with families and people with Barth syndrome?
- 5. What are the participant and family perceptions of research and any important potential barriers to participation?

The primary outcome to be measured is whole body oxygen consumption during peak bike ergometry exercise (i.e. peak VO₂). Improved quality of life is an overarching goal, principally through improved muscle function and is an important secondary outcome. A broad range of biochemical, mitochondrial and clinical readouts has also been selected as secondary outcome measures (see section 4.6) including cardiolipin ratio on which this work is predicated.

This study would also aim to look at many aspects of the practicality and robustness of study design.

4. Plan of Investigation

4.1 Study schema

4.2 Trial design

This study is a double-blinded, randomised, placebo-controlled crossover study. Treatment will be given in two 4 month long phases with a minimum of one month washout period between these where no treatment is given. Participants will be followed up as part of the study for one month after the end of second treatment period.

After phase 1 treatment has been completed by participants, a decision will be made by the Data Monitoring and Safety Committee as to whether an interim analysis should be conducted to assess the efficacy of phase I treatment. If so, confidential un-blinding will be performed by the study statistician to assess the response to bezafibrate. If an improved peak VO₂ (primary outcome) is demonstrated in \geq 50% of participants receiving bezafibrate, phase 2 of the study will commence as planned. If no response is demonstrated, or a response is demonstrated in less than 50% of participants receiving bezafibrate, phase 2 of the study will not go ahead and the study will finish.

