4.6.1 Primary outcome

The primary outcome measure is peak oxygen consumption on bicycle ergometry (i.e. peak VO_2), because this outcome is strongly associated with activity intolerance and may well correlate with subjective fatigability which we believe to be the most important determinant of quality of life in these patients. Peak VO_2 will be assessed at baseline and in the final week of each treatment phase.

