5.4 Duration of treatment period

The duration of the treatment period will be for a minimum of 9 months in total: 4 months of bezafibrate followed by 4 months of placebo (or vice versa), with a minimum washout period of one month in between, where no treatment is given between the two treatments.

If the DMSC deem it necessary for an interim analysis after the first phase of treatment and no effect of bezafibrate is found, the study may not continue on to the second phase. If this happens, the duration of treatment will be four months.

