6.3 Frequency of analyses

The primary analysis will take place when follow-up is complete for all recruited participants. After phase 1 treatment has been completed by participants, a decision will be made by the Data Monitoring and Safety Committee as to whether an interim analysis should be conducted to assess the efficacy of phase I treatment. If so, confidential un-blinding will be performed by the study statistician to assess the response to bezafibrate. If an improved peak VO₂ (primary outcome) is demonstrated in \geq 50% of participants receiving bezafibrate, phase 2 of the study will commence as planned. If no response is demonstrated, or a response is demonstrated in less than 50% of participants receiving bezafibrate, phase 2 of the study will not go ahead and the study will finish.

The DMSC will receive periodic reports on all adverse events to a timetable that the committee will set (together with the information about the medicinal product received if desired), together with any additional analyses the committee request.

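### The phase 1 go/no-go rule counts improvers on bezafibrate alone and ignores the randomised placebo arm, and the sections disagree on whether and how it binds

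*Protocol*

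**What the plan says.** Sections 4.2 and 6.3 of the Protocol carry the same rule. It is conditional at the outset: after phase 1, "a decision will be made by the Data Monitoring and Safety Committee as to whether an interim analysis should be conducted". If the analysis is held, the study statistician is unblinded in confidence. The go criterion is: "If an improved peak VO₂ (primary outcome) is demonstrated in" at least 50% "of participants receiving bezafibrate, phase 2 of the study will commence as planned". The no-go criterion is no response, "or a response is demonstrated in less than 50% of participants receiving bezafibrate, phase 2 of the study will not go ahead", and the study then finishes. Neither section gives a minimum change, a reference measurement or a comparison with placebo.

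Two other sections describe the same decision differently:

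- Section 5.4 says that if the DMSC wants the analysis and "no effect of bezafibrate is found, the study may not continue on to the second phase".
- Section 1 (Trial summary) says that after the first phase "the study statisticians will be unblinded to the treatment arms and will then assess whether or not there is evidence of efficacy" for the primary outcome, with no mention of a DMSC decision.

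On the data available, section 4.6.1 says peak VO₂ "will be assessed at baseline and in the final week of each treatment phase". On allocation, section 1 says "Half of the participants will take bezafibrate first, the other half will take placebo first". Section 4.7 expects 12 to 15 participants.

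**The concern.** The trial is placebo-controlled, and its first question in section 3 is the effect of bezafibrate compared with placebo. Section 4.3(a) relies on randomisation to protect the phase 1 comparison if phase 2 does not take place. Yet the rule that decides whether phase 2 takes place is an uncontrolled count in about 6 to 8 participants. Anything that shifts peak VO₂ over four months in both arms, such as growth, familiarity with the test or the course of the disease, enters the count as if it were a drug effect. The protocol gives neither the size nor the direction of such a shift.

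The crossover is at stake. A wrong stop removes the within-subject comparison on which the sample size rests, and section 2 counts only 18 UK candidates, so it would be hard to repeat. The wording adds a second problem: the DMSC cannot tell from the protocol whether the rule binds, or whether the trigger is a responder percentage or the absence of an effect.

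**Working it through.** **The plan's own figure.** Section 4.7 gives 80% power at 0.90 SD with 12 participants, two-sided alpha 0.05. A paired t-test with noncentrality 0.90 × √12 = 3.12 gives 81.0% (11 df) or 80.2% (10 df), so the figure reproduces if the SD is that of the within-subject difference. If it is the within-subject SD, as labelled, the SD of the difference is √2 times larger and power is 52%. The effect with 80% power is then 0.889 × √2 = 1.26 within-subject SD. That labelling is a separate matter; 1.26 is used below as the crossover's 80% point. The protocol gives no pass probability for the phase 1 rule.

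**Inputs.** Half of 12 to 15 gives m = 6, 7 or 8 on bezafibrate in phase 1. Baseline is the only prior within-person value, and no threshold is stated, so the plain reading of improved is any rise from baseline. Assumption: independent normal test-retest noise with within-subject SD 1.

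**Formula.** With true mean shift δ in within-subject SDs, one participant rises with probability p = Φ(δ/√2). The rule passes if at least k = ⌈m/2⌉ of m rise: P(go) = Σ_{j≥k} C(m,j) p^j (1−p)^(m−j).

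**Inert drug, no drift** (p = 0.5):

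- m = 6: (20+15+6+1)/64 = 42/64 = 65.6%
- m = 7: 64/128 = 50.0%
- m = 8: (70+56+28+8+1)/256 = 163/256 = 63.7%

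**Common shift, m = 6** (sizes assumed, not from the protocol):

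- Drift +0.5 SD, inert drug: p = 0.638, P(go) = 86.9%.
- Drift +0.5 SD, drug that harms by 0.5 SD: net shift 0, P(go) = 65.6%.
- Natural decline of 0.9 SD, drug that fully offsets it: net shift 0, so it is stopped 100 − 65.6 = 34.4% of the time.

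**What a placebo comparison does.** As an illustration with 6 per arm, suppose more improvers were required on bezafibrate than on placebo. An inert drug then passes 38.7%, 38.5% and 37.6% of the time when the common chance of a rise is 0.5, 0.6 and 0.7. The present rule gives 65.6%, 82.1% and 93.0%. The sensitivity to drift disappears.

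**Baseline-adjusted difference, 6 v 6.** With test-retest correlation ρ (assumed 0.5 to 0.9), the residual variance after adjustment is 1 + ρ in within-subject units. The standard error is about √((1+ρ)/3), slightly larger once chance baseline imbalance is allowed for, with 9 df. Simulation of that analysis (200,000 runs per cell, no drift) gives:

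| ρ | Power at 1.26 SD | P(difference > 0) at 0.90 SD | P(difference > 0) at 1.26 SD |
|---|---|---|---|
| 0.5 | 32.8% | 88.7% | 95.3% |
| 0.7 | 29.7% | 87.1% | 94.4% |
| 0.8 | 28.5% | 86.6% | 93.8% |
| 0.9 | 27.3% | 85.7% | 93.4% |

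The present rule with m = 6 and no drift continues 95.6% of the time at 0.90 SD (p = 0.738) and 98.7% at 1.26 SD. The difference rule passes an inert drug 50% of the time, with or without drift.

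**The case against.** The strongest reply is that passing an inert drug costs little here. A go only continues the planned double-blind crossover; it claims no efficacy and does not raise the final type I error. Having no gate at all would pass an inert drug every time. The rule also applies only if the DMSC asks for the analysis, and section 6.3 lets the committee request further analyses, which could include placebo data. All of this stands, and it is why the false-go rate is not the main harm.

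It is also fair that the drift sizes are assumptions. Appendix 1 plans practice on the bike, entry requires a stable cardiac condition, and growth matters less if peak VO₂ is expressed per kilogram, which the protocol does not say. Any rise from baseline is an inference, and an analysis plan could set a threshold that lowers the pass rates. A threshold would not bring placebo into the rule, however.

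Four stronger readings are tempting and are not supported:

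- **The rule cannot tell drug from no drug.** Without drift and with 6 on bezafibrate it passes 66% for an inert drug and 96% at 0.90 SD.
- **An inert drug passes two times in three.** That is right for 6 and nearly so for 8, but it is 50% for 7.
- **Growth or learning pushes the rate up.** The direction is unknown, and disease progression would push it down.
- **A go tells families that most on bezafibrate improved.** Unblinding is confidential, at least half is not most, and continuation may simply mean that no interim analysis was held.

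**Conclusion.** The concern holds as a should-fix. Sections 4.2 and 6.3 set a stop/go rule that leaves out the concurrent randomised comparator, so a change common to both arms can decide whether the crossover is completed. On the plain reading and without drift, the inert-drug pass rate is 50 to 66% depending on arm size. With 6 on bezafibrate, an assumed drift of +0.5 SD raises it to 87%, and an assumed decline of 0.9 SD stops a fully offsetting drug 34% of the time. A wrong stop leaves about 6 v 6 with roughly 27 to 33% power at 1.26 within-subject SD. These figures rest on normal noise, any rise counting as improvement, and a test-retest correlation of 0.5 to 0.9.

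The conflict between sections needs no calculation. Sections 4.2 and 6.3 bind on fewer than 50% responders, section 5.4 is permissive on no effect being found, and section 1 makes the unblinded look unconditional.

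**What to change.** In sections 4.2 and 6.3, base the DMSC's phase 1 efficacy assessment on the baseline-adjusted bezafibrate-minus-placebo difference in peak VO₂ with its confidence interval, and present it as non-binding advice. Reconcile sections 1, 4.2, 5.4 and 6.3 to that one rule, including the condition that the look takes place only if the DMSC asks for it.

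The cost is protocol wording and a matching line in the DMSC's terms of reference; no new data are needed. The downside should be stated openly. With no drift and 6 per arm, a plain difference-above-zero rule continues about 86 to 89% of the time at 0.90 within-subject SD against 96% now, and about 93 to 95% against 99% at 1.26 SD. Non-binding status, or a more lenient margin than zero, limits that loss. What is gained is that common drift no longer affects the decision.
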